9.5 Compliance and Missing Data

Based on preliminary work and other similar published interventions, 10% dropout is expected and the sample size was calculated to account for this rate. Phone, email, and/or text message reminders regarding assessments will be used to minimize dropout rate. Compliance with the intervention program will be evaluated by examining attendance at sessions and utilization of the app. All subjects will be asked to complete assessment regardless of their attendance at weekly sessions.

10. Human Subjects

10.1 Subject Population

Phase 1 participants will be 20 AYA survivors of childhood cancer and Phase 2 participants will be 88 AYA survivors of childhood cancer. Inclusion criteria for Phase 1: (1) any diagnosis of cancer prior to age 21; (2) current age 13 to 25; (3) off-treatment. Exclusion criteria for Phase 1 are: (1) non-English speaking; (2) significant developmental delay per patient, parent, or physician report; and (3) pregnant per patient report. Inclusion criteria for Phase 2: (1) any diagnosis of cancer prior to age 21; (2) current age 13 to 25; (3) off-treatment for at least 6 months. Exclusion criteria for Phase 2 are: (1) medical contraindication to exercise according to physician or physician's designee (form to be completed by patient's primary physician, oncologist, or physician's designee); (2) non-English speaking; (3) current activity level exceeding CDC guidelines for activity (60 min of moderate-vigorous exercise/day for 5+ days/wk including 3+ days of vigorous-intensity activities and 3+ days of muscle-strengthening activities and 3+ days of bone-strengthening activities for children <18 and 150 min of moderate-vigorous exercise or 75 min of vigorous exercise/wk and 2+ days of muscle-strengthening activities for adults \geq 18); (4) significant developmental delay per patient, parent, or physician report; and (5) pregnant per patient report. The CDC guidelines are used to determine exercise prescription in our intervention; individuals already exceeding the guidelines would be unlikely to benefit from participating. The Rutgers CINJ LITE program maintains a contact list of approximately 300 CCS, who receive regular newsletters and other mailings. Nearly half of the patients in the LITE program were seen at CINJ for follow-up care in 2010 and 2011. The approximate age distribution of LITE participants is: 0-8 years old = 6%; 9-12 years = 17%; 13-17 years = 29%, and aged 18 or older = 50%. This suggests that approximately 79% of LITE patients or 237 patients will be eligible for screening. With a conservative enrollment rate of 30% (we had 39% in our preliminary work using one source of survivors; other similar studies have reported enrollment rates from 27-85%⁵¹⁻⁵⁴), we could enroll about 71 patients per year, reaching our accrual goal of 88 in 18 months.

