5.1 Inclusion Criteria

Phase 1: A patient is eligible for enrollment if all of the following criteria are met:

- 5.1.1 Any diagnosis of cancer prior to age 21
- 5.1.2 Current age 13-25
- 5.1.3 Off treatment
- 5.1.4 For patients < 18 years, parents must give informed consent and patient must give assent. Patients ≥ 18 must give informed consent.

Phase 2: A patient is eligible for enrollment if all of the following criteria are met:

- 5.1.5 Any diagnosis of cancer prior to age 21
- 5.1.6 Current age 13-25
- 5.1.7 Off treatment for at least 6 months
- 5.1.8 For patients < 18 years, parents must give informed consent and patient must give assent. Patients ≥ 18 must give informed consent.

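### Section 10.1 presents the total yield of the LITE contact list (30% of 237 = 71) as a yearly rate, and the 237 includes adults above the age limit of 25

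*Combined protocol and SAP*

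**What the plan says.** The accrual argument is in section 10.1 (Subject Population). It starts from one source: "The Rutgers CINJ LITE program maintains a contact list of approximately 300 CCS, who receive regular newsletters and other mailings". It gives the age distribution as "0-8 years old = 6%; 9-12 years = 17%; 13-17 years = 29%, and aged 18 or older = 50" per cent and concludes: "This suggests that approximately 79% of LITE patients or 237 patients will be eligible for screening". It then applies a 30% enrollment rate, which it calls conservative. For comparison it cites 39% from the preliminary work and 27% to 85% from similar studies. The result is that "we could enroll about 71 patients per year, reaching our accrual goal of 88 in 18 months".

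The Phase 2 age criterion in section 5.1 is "5.1.6 Current age 13-25", and section 10.1 repeats that range. Section 5.6 says that Phase 2 invitations go by mail, using the existing LITE list, to patients in that age range or their parents.

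Sources outside this calculation are named without numbers. Section 3 names Hackensack University Medical Center as a site. Section 5.5 lists physician and staff referral, flyers, a web page, social media and university email lists. Section 4.2 allows two to three years for Phase 2 recruitment and data collection.

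**The concern.** Two features of the calculation push the projection upward.

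- **A stock is labelled as a flow.** The list is a set of people. Applying an enrollment rate to it gives the number expected to join when the list is invited. Someone randomized in the first year cannot be randomized again in the second. An annual rate would need a figure for new list members each year, or for the yield from re-inviting people who declined. The section gives neither.
- **The pool is not cut at the upper age limit.** The 79% adds the 13 to 17 band to an open-ended adult band. Anyone over 25 in that band is ineligible and, under section 5.6, would not be mailed.

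This is the only quantified argument in the documents that 88 can be reached and in what time. If it is wrong, the plan does not show how much of the target must come from outside the LITE list.

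**Working it through.** **Inputs.** All are from section 10.1 except the age limit, which also stands in section 5.1: list of 300; 13 to 17 years 29%; 18 or older 50%; 9 to 12 years 17%; planned rate 30%; preliminary rate 39%; goal 88; age limit 25.

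**1. The plan's own figure.**
- Pool: 300 × (0.29 + 0.50) = 237, as stated.
- Yield: 237 × 0.30 = 71.1, as stated.
- There is no time term in either line, so the 71 is a total.
- The listed bands add to 6 + 17 + 29 + 50 = 102%. Taking 100% − 23% = 77% gives a pool of 231 and a yield of 69, so the excess hardly matters.

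**2. Against the goal.**
- Shortfall at 30%: 88 − 71 = 17.
- Enrollment rate needed from the full 237: 88 / 237 = 37.1%.

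**3. With the age limit applied.** The list holds 300 × 0.29 = 87 people aged 13 to 17 and 300 × 0.50 = 150 aged 18 or older. The documents do not say what share *s* of the 150 are 25 or younger, so *s* is an assumption. Pool = 87 + 150 × *s*.

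| Assumed *s* | Pool | Yield at 30% | Yield at 39% |
|---|---|---|---|
| 100% | 237 | 71 | 92 |
| 75% | 200 | 60 | 78 |
| 50% | 162 | 49 | 63 |
| 25% | 124 | 37 | 49 |

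**4. Share needed at the preliminary rate.** 88 / 0.39 = 225.6 people; 225.6 − 87 = 138.6 adults; 138.6 / 150 = 92%. At 39% the list reaches 88 only if at least about 92% of the adults are 25 or younger.

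**5. Could ageing-in supply the annual flow?** Assume the 9 to 12 band is evenly spread by age.
- Band size: 300 × 0.17 = 51, so 51 / 4 = 12.75 turn 13 each year.
- Enrolled at 30%: 12.75 × 0.30 = 3.8 per year.
- Over 18 months: 3.8 × 1.5 = 5.7, total 71.1 + 5.7 = about 77.
- Over three years: 3.8 × 3 = 11.5, total about 83.

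Both totals use the full 237, with nobody over 25 removed, and both stay below 88.

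**The case against.** The strongest reply is that the sentence is a rough check in the Human Subjects section of a pilot, built on a rate that the plan calls conservative. Much of that reply stands, and it rules out several stronger readings.

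- **That the list can give no more than 71.** This holds only at 30%. At 39% the uncut pool gives 92, and the cited range for similar studies goes up to 85%. However, the projection uses 30%, and the margin at 39% is gone once more than about 8% of the adults are over 25.
- **That the list is closed.** The documents say only that it is maintained, and the 9 to 12 band will age in. Under the even-spread assumption, though, that adds only about 6 over 18 months.
- **That the trial cannot reach 88.** The second site, referral, flyers and social media lie outside the calculation and could supply the rest. They carry no numbers, so the documents show neither that they will nor that they will not.
- **That the sample size and power depend on this projection.** Section 9.2 sets 88 from 80 evaluable patients and 10% attrition and does not cite the accrual estimate. The projection bears on whether 88 can be reached, not on how it was chosen.
- **That Aim 2 inherits a wrong benchmark.** Section 9.4 analyses enrollment descriptively and sets no numerical threshold for it, and the section 5.6 mailing is already limited to ages 13 to 25.

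Three smaller points also do not count against the plan. At 71 per year, 88 would take 88 / 71 × 12 = 14.9 months. That fits within 18, and recruitment in waves could explain the rounding. The other Phase 2 exclusions are not applied to the 237, but the text claims only eligibility for screening, and the enrollment rate may absorb those losses. Phase 1 also draws on LITE patients, but nothing bars its participants from Phase 2, so no depletion is shown.

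None of this supplies a yearly inflow or removes the adults over 25 from the 237.

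**Conclusion.** The projection is wrong as written on two counts: a total is called a yearly rate, and the pool extends past the age limit. At the planned 30% the existing list yields about 71 or fewer, 17 or more short of 88. The 71 needs no assumption beyond the plan's own inputs. The lower figures, about 60 and 49, rest on assumed shares of 75% and 50% of adults aged 18 to 25.

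The claim that the list reaches 88 in 18 months is therefore unsupported. A reader might go on to infer that the trial cannot accrue 88. The documents do not support that, because they name further sources whose yield is unknown.

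The section should be corrected, but this is not critical. No endpoint, analysis or randomization rule depends on it, and section 9.2 states that the primary aim is feasibility.

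**What to change.** In section 10.1:

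1. Replace the 237 with a count of LITE list members who are aged 13 to 25.
2. Give 30% of that count as a total yield from the list, and drop the yearly label.
3. State the expected yearly inflow to the eligible part of the list, from ageing-in and new patients.
4. Add the expected numbers from Hackensack, referral, flyers and social media that are needed to reach 88.
5. Restate the accrual time from those figures.

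The cost is a query of the clinic list, one rewritten paragraph and probably a less favourable projection. Design and conduct do not change.

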10.2 Potential Risks

Potential risks are considered minimal. In Phase 1, the risks are the same as encountered in daily life. The interviews will focus on app design and development and individuals' perceptions of its usefulness in daily life. In Phase 2, increased physical activity may result in muscle soreness or injury; however, each participant will be required to have their physician, oncologist, or physician's designee complete a form prior to enrollment clearing the participant for engagement in a physical activity program. Physical fitness testing will be done by trained personnel. [name], a mentor and Co-Investigator on this project, is a certified strength and conditioning specialist and will provide expert guidance to [name] for hiring and training qualified personnel. It should be noted that the fitness tests utilize standard exercise testing protocols. To protect the participants against risks of injury, the trainer will have adequate experience and training in working with AYAs, with a preference for certification in working with cancer survivors. All exercises will be age-appropriate and the intensity can be modified according to individual comfort. Further, the trainer will have each participants' emergency contact information with them during all sessions in the event that an injury occurs. Adolescents and young adults may feel uncomfortable answering

questions regarding physical or emotional functioning, and will be free not to answer any question. Participants are permitted to refuse to participate in any aspect of the research, and may withdraw from the study at any time for any reason. To minimize risk of breach of confidentiality when using the app, data will be stored in an encrypted and cached environment on the device itself and securely transmitted to our servers for downloading by researchers. All data storage and transmission will be encrypted and logged for audit-ability to meet the applicable HIPAA standards. Questionnaire data will be coded with an ID number and stored in locked filing cabinets that are only accessible to appropriate research personnel. The key linking ID number and personal identification will be kept separately from research files. The mHealth app and private Facebook group will be kept private only to individuals in the study. Messaging between participants will be monitored by the PI and trainer, who will remove any negative or questionable comments as soon as discovered (i.e., if a participant sends a message teasing another participant or using a curse word, it will be removed as soon as discovered). Confidentiality will be further maintained by reporting only group data in study publications and presentations.

10.3 Consent Procedures

Patients and parents will be informed of the study by the study team via letter, flyers, in person at clinic, or telephone. The PI or a trained member of the study team will explain the study to the potential subject and answer all questions. We will obtain informed assent from patients ages 13-17 and consent from their parents; we will obtain informed consent from patients ages 18-25. Participants will be given a signed copy of consent/assent documents, along with the phone numbers of the investigators to call if they have questions.

10.4 Potential Benefits

There are no direct benefits for participating in Phase 1, design of the mobile app. Although not guaranteed, the potential benefits of participating in Phase 2, the randomized trial of the technology-enhanced intervention, include improved cardiorespiratory fitness, muscular fitness, health-related quality of life, and fatigue. All participants, including those in the waitlist control, will have the opportunity to participate in the exercise program for free. This study has the potential to yield important information regarding health promotion behaviors for AYA survivors of pediatric cancers, an important but understudied population.

10.5 Risk-Benefit Ratio

The minimal risk involved in this study is reasonable in relation to the anticipated benefits of the research. Alternatives to participating are not participating; choosing not to participate does not affect patients' medical care. Results of the proposed research will inform the feasibility and preliminary effectiveness of a technology-enhanced fitness intervention to improve physical fitness in AYA survivors of pediatric cancers. Information on the incorporation of a mHealth application is particularly novel and will guide our understanding of the application of mHealth technology to this area of research. Data from this study will be used to generate a sample size estimate and refine research procedures for a future R01 application that will evaluate the efficacy of a technology-enhanced fitness intervention for AYA cancer survivors. The benefit of improved health outcomes outweighs the minimal risks associated with participation. This approach may also inform interventions to improve motivation for other healthy behaviors in this population.

